Protocol Title: Study of Colorectal Cancer Screening Options

Study Protocol: 5/09/2019

PI: [name]

NCT05987709

1. Protocol

Title: Study of Colorectal Cancer Screening Options

PI: [name]

2. Objectives

We propose to evaluate Guardant Health's commercially available colorectal cancer screening assay (Guardant SHIELD) in individuals who are not up to date with CRC screening.

Primary Objective (or Aim)

Assess colorectal cancer screening completion among patients who are non-adherent after receiving stool test outreach, who have an upcoming clinical appointment, and who are offered a commercially available colorectal cancer blood test versus usual care (i.e. reminder to complete stool testing during their clinical appointment).

Secondary Objectives (or Aim)

Assess patients' and providers' perceived confidence in the test (based on available test performance characteristics) and willingness to obtain/offer the test on an on-going basis, based on qualitative interviews; assess preliminary rates of follow-up colonoscopy completion (after an initial abnormal test result) among participants allocated to the blood test vs. usual care condition.

3. Background Information and Rationale

Blood-based tests for colorectal cancer detection are thought to offer many advantages over stool-based and endoscopy-based tests. Such tests can be easily completed during in-person clinic visits and can be combined with other blood draws. Such tests may be particularly acceptable for patients who forgo stool-based testing options due to the 'yuk' factor. While blood-based tests will likely produce greater colorectal cancer screening adherence than stool-based testing and endoscopy options, there is little empirical data to support this claim.

4. Study Design

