1. One (1) blood sample will be collected in each of 200 unique patients who (a) received, but did not complete, a FIT in the past 3-9 months, and (b) have an upcoming appointment at KPNW in the next 2-6 weeks.
2. Forty (40) mL of whole blood will be collected per sample using 4, 10mL Streck tubes as part of the Blood Collection Kit ("Kit") provided by Guardant.

3. Guardant's Test Requisition Form (TRF) will be completed (with the PI information and participant ID number) for each sample and placed in the Kit.
4. Each sample will be packaged and the corresponding TRF included in the Kit. The Kit will be shipped to Guardant overnight using the pre-paid, pre-addressed FedEx Clinical Pak.
5. Samples received by Guardant greater than 7 days from the time of receipt may be subject to cancellation per the CLIA-certified lab protocol.

No identifiable patient information will be placed on the tube – Only a study sample ID will be on the tube when sent to Guardant Health's lab.

Blood Sample Processing (CLIA line)

Once received Guardant will test the blood samples. Guardant will test samples using its colorectal cancer screening assay in its CLIA-certified lab. A final report for each sample will then be provided to the investigator(s) via its online portal within approximately 14 days of sample receipt. Guardant will cover the cost of processing and reporting up to 200 tests.

Data Collection

The study analyst will provide certain clinical data to Guardant (within 120 days of the 200th intervention patient enrolled, and blood sample received), the details of which follow:

- Patient ID
- Age at study entry
- Cohort assigned to
- GH colorectal cancer screening test result (if applicable)
- FIT test result after randomization (if applicable)
- Time between colorectal cancer screening test result offer and screening test completion
- For those with positive screening test, was colonoscopy completed?
 - If yes, time between positive test result and colonoscopy
 - If yes, colonoscopy outcome (CRC, advanced neoplasia, non-advanced neoplasia, negative, incomplete)

Qualitative Data Collection

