Results from the commercially available blood test will be provided to the patient (through mail/email or phone call). A copy of the final report will be scanned into the patients EMR. In addition, participants whose test result is abnormal will be notified by the GI department, whose staff will facilitate the referral and scheduling of a follow-up colonoscopy (a recommended screening at KPNW). Participants whose tests result is normal will receive a letter that includes a number to call if they have any questions.

The blood sample will only be tested for markers of colorectal cancer; there is no known risk of incidental findings. The laboratory conducting the test is Clinical Laboratory Improvement Amendments (CLIA) certified.

d. Data and/or Specimen Banking
 N/A

8. Privacy, Confidentiality and Data Security

Information obtained in this study will include protected health information of the patients. The identity of the patients will not be part of the study. No personally identifiable information will be shared outside the clinic. All reports, forms, or articles related to this study will be prepared such that no individual patient can be identified. Samples will be coded with a study ID number to protect patient confidentiality. Only the authorized CHR study personnel will have access to the link between the patient's identifiable information and the study ID.

Collection of sensitive data will not occur as a part of this study.

Describe the plan for storage of data and/or specimens.

In order to minimize the risk of loss of confidentiality, all records related to study data will be kept in locked cabinets. Access to study information will be restricted to authorized research personnel. A password system will be used to control access to all information stored on a secured computer. All residual blood samples will be discarded at the end of the study.

For the qualitative interview component of this study, the interviews with both patients and providers will be conducted via telephone using password encrypted devices and software (e.g. CHR laptop using Microsoft Teams calling functions) and stored behind CHR firewalls within project specific folders. De-identified audio transcripts will be retained indefinitely.

Study data will be retained and destroyed in compliance with the study contract.

Collection of data from subjects electronically

N/A

Does this study involve the disclosure of PHI to a collaborator?

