Because this study will not involve treatment, adverse events are unlikely to occur. However, as a safeguard, the clinical research coordinators, and the principal investigator will review study data; study results (when available); complaints about the research; and will report any adverse events or unanticipated problems involving risk to patients to the Institutional Review Board. Adverse Events of any sort reported to the project team and investigator will also be characterized by type and number. Standard risks associated with blood draws include pain, bruising in the area from where the blood is taken, redness and swelling of the vein, infection, dizziness and a rare risk of fainting. These risks will vary from person to person. The healthcare staff will follow normal clinical practices to ensure sterility and safety. Study participants undergoing the blood draw will be advised to talk to their doctor about any side effects while taking part in this study. Many patients will be getting their blood drawn for non-study purposes, thus, only adverse events associated with study blood draws will be attributed to the study. Adverse events associated with colonoscopy (perforation, bleeding) are extremely rare; any adverse events associated with colonoscopy will not be attributable to the study because colonoscopy is part of standard care.

Plans for the Patients at the End of the Protocol

Patients will continue to follow their schedule of recommended screenings regardless of their participation in the study. Any patient who experiences problems from participating in this study will be provided all appropriate medical care and the study staff will follow their progress and give appropriate recommendations for on-going screening. However, no further contact with patients is anticipated during or after completion of the study (beyond potential recruitment and participation for the qualitative interview component).

10. Risks and Benefits

a. Risks to Subjects

There are minimal risks and discomforts to participating in this study. Collection of blood involves potential risk of pain or discomfort, redness, bruising or localized infection at the site of the needle stick. Patients will be instructed to alert staff for any complications resulting from the blood draw.

Patients may feel uncomfortable with questions asked during the qualitative portion of the study. We will be clear that answering all questions will be optional. There may be risks of data breach.

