There are no additional risks or discomforts to patients in this study.

In the unlikely event that a patient experiences physical injury or illness because of participating in this research study, medical care will be made available at the clinical site of sample collection.

b. Potential Benefits to Subjects

Patients will not benefit directly from involvement in the study. However, the general colorectal cancer screening-eligible patient population may benefit from the ease of a blood test. Some patients may benefit from obtaining the blood test and obtaining a follow-up colonoscopy.

11. Economic Burden to Subjects

No cost will be incurred by the subjects for participation in this study.

12. Compensation to Participants

Patients will not be compensated for participation.

Patients participating in the qualitative interview will be offered a \$25 gift card as appreciation for their participation.

13. Resources Available

N/A

14. Additional Approvals

N/A

15. Drugs or Devices

N/A

16. Multi-Site Research

N/A

17. Community-Based Participatory Research

N/A

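### Section 9 rules in advance that no colonoscopy adverse event is attributable to the study, with no exception for a colonoscopy prompted by an abnormal study blood test

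*Protocol*

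**What the plan says.** **Attribution.** Section 9 calls colonoscopy complications extremely rare and then states that "any adverse events associated with colonoscopy will not be attributable to the study because colonoscopy is part of standard care". The rule has no conditions: it applies whichever test led to the colonoscopy and whichever arm the patient is in.

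**Reporting.** The same paragraph says that the coordinators and the principal investigator "will report any adverse events or unanticipated problems involving risk to patients to the Institutional Review Board", and that "Adverse Events of any sort reported to the project team and investigator will also be characterized by type and number". Neither sentence is limited to events judged attributable.

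**The route to colonoscopy.** Under section 7c, patients with an abnormal blood test are notified by the GI department, "whose staff will facilitate the referral and scheduling of a follow-up colonoscopy".

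**Colonoscopy as a study outcome and benefit.** The secondary objectives in section 2 include to "assess preliminary rates of follow-up colonoscopy completion (after an initial abnormal test result) among participants allocated to the blood test vs. usual care condition". Section 7a makes progression to endoscopy, and its findings, exploratory endpoints. The data list in section 7 (Data Collection) has completion, time to colonoscopy and "colonoscopy outcome (CRC, advanced neoplasia, non-advanced neoplasia, negative, incomplete". Section 10b says: "Some patients may benefit from obtaining the blood test and obtaining a follow-up colonoscopy".

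**Risks.** Section 10a names the blood draw, discomfort with interview questions and data breach, and then states that there are no others. Colonoscopy is not named.

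**The concern.** The reason given for the rule is that colonoscopy is standard care. That describes the procedure, not why a given patient had it. Patients enter because they were sent a FIT 3-9 months earlier and did not return it. If such a patient is randomised to the blood test offer, has an abnormal result and is referred, the randomised intervention is at least a plausible cause of the colonoscopy and of any complication. Whether it was the cause in a given patient calls for individual assessment, and the rule removes that assessment before any event has occurred.

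The protocol is also asymmetric. The possible gain from a follow-up colonoscopy is credited to participation, and its completion and findings are reported as results, while its possible harm is excluded from attribution. A report from this trial could truthfully say, under its own rule, that no colonoscopy event was study-related, whatever happened. A reader weighing a screening offer would take that as evidence when it is a consequence of the definition.

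**Working it through.** The plan gives no figure on this point to reproduce: no expected uptake or positivity, no colonoscopy completion rate and no complication rate. The check is therefore a comparison of passages, followed by a calculation for scale on assumed inputs.

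**1. What would happen to a complication after a positive study blood test**

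| Step | What the protocol provides | Result |
|---|---|---|
| Does the event reach the team? | Outcomes come from chart review in both arms (section 5f). The colonoscopy items listed in section 7 are completion, timing and findings. Section 10a has patients alert staff to blood-draw complications. Section 9 advises those having the draw to raise side effects with their own doctor and expects no further contact beyond the interviews. | Possible, but no listed item asks for it |
| If it does, is it counted? | "Adverse Events of any sort reported to the project team and investigator will also be characterized by type and number" | Yes |
| Is it reported to the IRB? | "will report any adverse events or unanticipated problems involving risk to patients to the Institutional Review Board" | Yes |
| Is it attributed to the study? | "any adverse events associated with colonoscopy will not be attributable to the study because colonoscopy is part of standard care" | Never |
| Is it compared between arms? | No tabulation of complications by arm is stated | Not planned in this document, though not prevented |

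So the rule fixes attribution at zero. It does not fix the count at zero.

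**2. Scale**

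The only input from the protocol is the ceiling of 200 blood tests (section 7). The others are assumptions, set wide:

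- blood tests done: 100 to 200
- positivity: 5% to 15%
- colonoscopy completion after a positive test: 50% to 100%
- complication rate per colonoscopy: 0.1% to 1%

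Colonoscopies after a positive blood test, n = tests × positivity × completion:

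- low: 100 × 0.05 × 0.50 = 2.5
- high: 200 × 0.15 × 1.00 = 30

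Expected complications = n × r:

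- low: 2.5 × 0.001 = 0.0025
- high: 30 × 0.01 = 0.30

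Chance of at least one = 1 − (1 − r)^n:

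- low: 1 − 0.999^2.5 = 0.0025, or 0.25%
- high: 1 − 0.99^30 = 0.260, or 26%

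Even at the high end, the chance of none or one is 0.99^30 + 30 × 0.01 × 0.99^29 = 0.740 + 0.224 = 0.964. The rule will probably touch no event or one. These figures cover colonoscopies after a positive blood test only; those after a positive FIT fall under the same rule and are not included.

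**The case against.** The strongest defence is that section 9 contains its own safeguard. Any adverse event goes to the IRB, and events of any sort that are reported are counted. A perforation known to the team would be visible, though labelled not attributable. This stands, and it rules out several stronger readings that a reader might infer:

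- **That colonoscopy harms are recorded as zero, or that the IRB would not hear of them.** The text does not say so. The rule governs attribution; the reporting sentences carry no attribution filter. The weakness is that they depend on the event reaching the team.
- **That a comparison between arms is prevented.** The rule covers both arms, including colonoscopy after a positive FIT, and a causality label does not stop tabulation by arm. It is fair to say only that no such tabulation is stated.
- **That a second sentence in section 9 confirms a wider exclusion.** The statement that "only adverse events associated with study blood draws will be attributed to the study" follows a remark that many patients will have blood drawn for non-study reasons. It separates study draws from other draws and does not address colonoscopy.
- **That the colonoscopy exists only because of the study test.** Participants were already due for screening and had been sent a FIT, and section 7c describes follow-up colonoscopy as a recommended screening at the health plan. Some would have reached colonoscopy anyway. That argues for assessing each case, not for excluding them all.
- **That this is the main or only serious harm of the intervention.** The protocol does not rank harms, and a falsely normal result is another conceivable one.

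It can also be said that the list in section 7 describes data sent to the funder and is not the full chart-review form. That is correct: it shows that no complication item is listed, not that none will be collected. The rarity of events limits the size of the issue but does not justify the rule, because a single event would be misclassified.

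**Conclusion.** The point holds as one about attribution. Section 9 settles causality in advance for every colonoscopy event, including one prompted by an abnormal study blood test, while sections 2, 7 and 10b treat that same colonoscopy as a study outcome and a possible benefit. Any such complication would be classed as unrelated without being assessed.

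The practical size is small: 0.0025 to 0.30 expected complications after a positive blood test, with a 0.25% to 26% chance of at least one. All inputs apart from the 200-test ceiling are assumptions. Neither the primary endpoint nor the exploratory endpoints are affected. What is affected is whether a statement that no study-related colonoscopy event occurred carries any information. The sentence should be changed because it is unsound and cheap to repair, not because many events are expected.

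**What to change.** Replace the attribution sentence in section 9 with:

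> Complications of any colonoscopy that follows a post-randomisation screening test (blood or FIT) will be collected by chart review in both arms, tabulated by arm and by the test that prompted the procedure, and assessed case by case for relatedness; events will be reported to the IRB with that assessment.

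The text should not preset a label such as possibly related for events after a positive blood test. That would be another verdict fixed in advance and would contradict the case-by-case assessment.

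Reconcile the risk list in section 10a with this text and with the benefit stated in section 10b, so that follow-up colonoscopy is treated alike on both sides.

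The cost is the wording change and one added item in a chart review already planned for both arms. The item should be checked against the scope of the usual-care waivers of consent and HIPAA authorization (sections 5f and 5g), which the protocol does not spell out. The safety statement becomes slightly less favourable.
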